## **16.0 Informed Consent**

Informed consent materials, including a model consent form; will be provided to each investigator. In compliance with Ascension Orthopedics, Inc. policy, no subject is to be enrolled in this study without adequate informed consent being provided or a waiver of consent granted by the ETHICS BOARD. The informed consent process should be documented in the subject's medical record. Failure to obtain, or improper documentation of, informed consent is in violation of Ascension policy and the study protocol unless

exempted by an ETHICS BOARD waiver. In the event of such an exemption, a release of Medical Records shall be obtained.

Some ETHICS BOARD's require modifications to the Informed Patient Consent form (IPC) to satisfy specific institutional requirements. Use of modified consent forms is permitted provided they meet the local requirements.

The investigator will solicit the informed consent of any patient meeting the selection criteria prior to surgery. The investigator will answer all questions the subject may have and will explain the following features of the study thoroughly including:

- The purpose of the study
- Possibility of failure and subsequent treatment(s)
- Alternative procedures
- Requirements of the study (follow-up visits),
- All of the Subject's rights as a subject in the clinical investigation.

If the patient agrees to participate in the study, either an IPC form as approved/required by each ETHICS BOARD or a release of medical records as appropriate must document this. One completed copy of the consent and/or release form is to be given to the patient, another placed in the hospital files if required. The original IPC form remains with the clinical investigator (i.e., within the CRF booklet or clinic chart). The **IPC is not forwarded to the Sponsor**. Once a Subject has executed the IPC documentation, they are considered a study subject.

Subject should sign and date the IPC form prior to any study required assessments or exams as described in Section 6.0 above, and prior to the day of surgery. However, if the IPC is signed on the day of surgery, then the source document must state that the subject

was given adequate time prior to the time of surgery to review and give consent. In such a case, the time the Subject signed the IPC form must be documented.

For the purposes of this study, the success or failure of the Product will be based upon the patient's clinical results as measured using the clinical and radiographic parameters detailed herein. Investigators should document each death using the Adverse Event/Withdrawal CRF.

## **17.0 Review of Source Documents**

---

Source data is all information, original records of clinical findings, observations, or other activities in a clinical trial necessary for the reconstruction and evaluation of the trial. Source data are contained in source documents Examples of these original documents, and data records include: hospital records, clinical and office charts, laboratory notes, patient completed evaluation forms, recorded data from automated instruments, copies or transcriptions certified after verification as being accurate and complete, magnetic media, x-rays, subject files, and records kept, at the laboratories, and at technical departments involved in the clinical trial.

The Investigator is responsible for ensuring that the data on the case report forms is consistent with the data in the source documentation. The Investigator may designate a medically trained designee to sign all forms **except** the Withdrawal form and the Adverse Event form. The Investigator must make source documentation available for monitoring by the Sponsor or delegate, the ETHICS BOARD, and other authorized government agencies. Failure or unwillingness to provide this access will disqualify the site and Investigator from participation in this clinical evaluation.

## **18.0 Record of Device Inventory**

---

This is a post market study and all devices are CE marked. Therefore inventory control is not a regulatory requirement.

**Confidential**

Protocol Date: May 27, 2013  
Amendment 1  
Revision 2

**Ascension Orthopedics**

CP-HRA-002

## **19.0 Sponsor Obligations**

---

### **19.1 Investigator Training**

All participating investigators will undergo training on the PyroTITAN™ HRA Shoulder prosthesis either through a hands-on training session or by a Sponsor approved training module.

### **19.2 Monitoring**

The Sponsor will designate qualified individuals to monitor the progress of the clinical investigation. The monitor(s) responsibilities include:

- Visiting the Investigator periodically to ensure the fulfillment of all obligations associated with the clinical investigation.
- Reviewing individual Subject records and other supporting source documentation, comparing those records with CRFs prepared by the Investigator and submitted to the Sponsor, and ensuring that data submitted to the Sponsor is accurate and complete.
- Maintaining a record of each on-site visit to an Investigator noting findings, conclusions, and actions taken to correct deficiencies.

### **19.3 Sponsor Study Termination**

Both the sponsor and the Investigator reserve the right to terminate the study at any time. Should this be necessary, both parties will arrange the procedures on an individual study basis after review and consultation. In terminating the study, Ascension Orthopedics and the Investigator will assure that adequate consideration is given to the protection of the patient's interests.

## **20.0 Changes to Investigational Plan**

---

No changes to this protocol with the exception of those of an emergent nature will be made without written consent from the sponsor and mutual agreement between the investigators and sponsor. The investigators, sponsor, and investigators' governing ETHICS BOARD will record all changes.

Applicable ETHICS BOARD approval will be obtained prior to implementation of changes in the Investigational Plan that may affect the scientific soundness of the investigation, or the rights, safety, or welfare of study subjects.

## **21.0 Confidentiality**

---

Information about study subjects will be kept confidential and managed according to the requirements of the country of the participating clinical investigator.

### **Data protection and data transfer**

In order to observe the confidentiality of personal data, each patient will be allocated a confidential identification code consisting of the investigator centre number and a 3 figures patient number.

CRF or other documents submitted to the sponsor will identify a patient by this identification code. Each investigator will keep in his file a screening Log and a patient identification list (including complete name and date of birth of each patient). To allow compliance with GCP principles, each patient will be asked for consent regarding the access to source documents for monitoring, audits, and inspections.

The Information Letter and Data Transfer Authorization form explain that the study data will be kept in an electronic form, confidentially, in accordance with the French law N°78-17. All the computerised data will be identified by "centre n°/ patient n°".

The information Letter and Data Transfer Authorization Form will specify that the sponsor representative and the competent authorities will have direct access upon request to the source documents related to the study, including medical antecedents, to check the accuracy of the data.

Study documents and records will be kept for at least 15 years after the end of the study by the investigator: this includes codes allowing the identification of patients, medical files and all the source data, the CRF, the queries, the patient's information letter and DTA, the copies of IEC and competent authorities approval (if necessary) and any other document pertinent to the study.

Integra LifeSciences Corp. will store all of the documents relating to the study throughout the lifespan of the product and for a minimum of 15 years:

- The text of the clinical protocol and its annexes;
- The EC opinion;
- The case report forms;
- The anonymised data in a database;
- The monitoring documents (correspondence, memos, etc.)

## **22.0 Withdrawal or Termination of the Clinical Investigation**

Any subject who wishes to withdraw from this investigation on his/her own accord and for whatever reason is entitled to do so without obligation and prejudice to further treatment. In addition, the Investigator may decide for reasons of medical prudence, to withdraw a subject. In either event, the Investigator will clearly document the date and reason(s) for the subject's withdrawal from this investigation in the clinic notes and should indicate whether or not he considers it related to the device.

Both the sponsor and the Investigator reserve the right to terminate the study at any time. Should this be necessary, both parties will arrange the procedures on an individual study basis after review and consultation. In terminating the study, Ascension Orthopedics and the Investigator will assure that adequate consideration is given to the protection of the patient's interests.

## **APPENDIX A**

## **CASE REPORT FORMS**

**Confidential**

Protocol Date: May 27, 2013  
Amendment 1  
Revision 2

**Ascension Orthopedics**

CP-HRA-002

# Statistical Analysis Plan

A Multi-center Outcomes Clinical Study of the PyroTITAN™ HRA Shoulder Implant in Humeral Head Resurfacing

Number: CP-HRA-002  
ST: ST1159  
Version: 1.0 05/Oct/2023  
Page: 2 of 19

## 1 LIST OF ABBREVIATIONS

Abbreviation	Definition
ADE	Adverse Device Effect(s)
ADL	Activities of Daily Living
AE	Adverse Event(s)
ANCOVA	Analysis of Covariance
ASES	American Shoulder and Elbow Surgeons Shoulder Score
CRF	Case Report Form(s)
DevD	Device Deficiency(ies)
DF99	Datafax Safety Database
EC	Ethics Committee
EQ-5D	EuroQol 5D
FAS	Full Analysis Set
FDA	Food and Drug Administration
FU	Follow-Up
ITT	Intention to Treat Population
LOCF	Last Observation Carried Forward
LSMean	Least Squares Mean
NA or N/A	Not Applicable
N (or n)	Total Sample Size (or subgroup sample size)

# Statistical Analysis Plan

A Multi-center Outcomes Clinical Study of the PyroTITAN™ HRA Shoulder Implant in Humeral Head Resurfacing

Number: CP-HRA-002  
ST: ST1159  
Version: 1.0 05/Oct/2023  
Page: 4 of 19

Abbreviation	Definition
NSAE	Non-Serious Adverse Event(s)
PP	Per-protocol Population
QoL	Quality of Life
S+N	Smith+Nephew Orthopedics
SADE	Serious Adverse Device Effect(s)
SAE	Serious Adverse Event(s)
SAP	Statistical Analysis Plan
SAF	Safety Analysis Set
TFL	Tables, Figures and Listing
USADE	Unanticipated Serious Adverse Device Effect(s)
VAS	Visual Analog Scale
WOOS	Western Ontario Osteoarthritis of the Shoulder index

## 2 INTRODUCTION

The following Statistical Analysis Plan (SAP) details the statistical considerations, including the data analysis methods, for the Study Protocol version 2, 27-May-2013. Related documents to this SAP are the Study Protocol, Case Report Form (CRF), and Tables, Figures and Listings (TFL) Templates Shells.

## 3 STUDY DESIGN

The study is a post market, multi-centre prospective, non-randomized, non-comparative, open investigation.

## 4 STUDY OBJECTIVES

### 4.1 Primary Objective

The primary objective is to determine success of the PyroTITAN™ HRA Shoulder Prosthesis as defined by no revisions, no device related complications requiring surgical replacement and freedom from chronic dislocation.

# Statistical Analysis Plan

A Multi-center Outcomes Clinical Study of the PyroTITAN™ HRA Shoulder Implant in Humeral Head Resurfacing

Number: CP-HRA-002  
ST: ST1159  
Version: 1.0 05/Oct/2023  
Page: 5 of 19

## 4.2 Secondary Objectives

The secondary objectives of this investigation are to evaluate the functionality, and radiographic performance of the PyroTITAN™ HRA Shoulder prosthesis.

## 5 STUDY ENDPOINTS

### 5.1 Primary Endpoint

The primary endpoint is a composite endpoint for clinical success.

Clinical requirements for success will be evaluated at 24, 60 and 120 months:

- Device remains implanted
- Absence of device-related complications requiring surgical replacement, removal, or augmentation of components
- Freedom from chronic dislocation

### 5.2 Secondary Endpoint(s)

To demonstrate postoperative functionality and radiographic performance at 2, 3, 4, 5, 8 and 10 years post treatment, as compared with pre-treatment results through:

- ASES Score improvement
- Patient satisfaction
- VAS Pain
- WOOS
- Constant Score
- EQ-5D Quality of Life Questionnaire

Radiographic and MRI requirements for success at the different time points:

- No evidence of device failure, specifically progressive migration or implant loosening
- Anatomic alignment is a criterion that may be included in the definition of success in some investigations

### 5.3 Exploratory Endpoint(s)

To demonstrate postoperative functionality at 2, 3, 4, 5, 8 and 10 years post treatment, as compared with pre-treatment results through:

- Range of motion

# Statistical Analysis Plan

A Multi-center Outcomes Clinical Study of the PyroTITAN™ HRA Shoulder Implant in Humeral Head Resurfacing

Number: CP-HRA-002  
ST: ST1159  
Version: 1.0 05/Oct/2023  
Page: 6 of 19

## 5.4 Safety Endpoint(s)

Adverse Events including, but not limited to:

- Infection
- Loss of fixation
- Breakage
- Dislocations
- Revisions

# 6 STATISTICAL CONSIDERATIONS

## 6.1 Determination of Sample Size

The following is the sample size justification taken from the study protocol V2, 27-May-2013:

The original sample size in this study was 150 enrolled subjects. Additional proof testing and improvements in the device inspection process were employed during the study, at which time it was determined that an additional cohort of subjects was necessary. We are now comparing a cohort of subjects enrolled after these changes to the original cohort of subjects.

With an expected attrition rate of 10% per annum, this will yield an evaluable sample size of 52 shoulders at ten years ( $150 * 0.9^{10} = 52.3$ , where 0.9 or 90% is the number expected to be retained from one year to the next). Based on past experience, we may obtain clinical follow-up on this number of shoulders, but we may obtain radiographic follow-up on as few as two-thirds of these shoulders (about 35 shoulders). This remaining number of evaluable shoulders with clinical and radiographic follow-up is adequate to establish a reliable ten-year survival estimate of survival for hemi arthroplasty (Dorey and Amstutz, 1986).

For the new cohort, the sample size is calculated based on the non-inferiority of the study device. The success rate for the study device is 96.1% from the original population and is used as reference rate. Therefore, for a conservative success rate of 96.1% of the study device is used in the study. The non-inferiority margin  $\delta$  of -0.033 is chosen in the study. 212 subjects are required to achieve  $100(1 - \beta) \% = 80\%$  power to detect non-inferiority at the Significance level of  $\alpha = 0.05$ . To account for 10% lost to follow-up, the total number of additional subjects is 237. Therefore, the estimated enrolment for the study will be 387 subjects.

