## **7.0 Revision/Re-operation**

---

Post-operative surgical procedures associated with the operative shoulder are categorized as Adverse Events. If a Subject undergoes any surgical procedure on the operative shoulder in which all of the original Pyro-Titan Resurfacing Shoulder implant components are retained (debridement etc), the Subject is not withdrawn from the study and all follow-up visits are maintained according to the Subject Management Schedule. If the Pyro-Titan Resurfacing Shoulder prosthesis implant is removed then the Subject is considered revised, is withdrawn from the study, an Adverse Event and Study Completion CRFs must

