**Ascension Orthopedics**

CP-HRA-002

be submitted to the Sponsor. The remaining study-related follow-up visits are not required in the case of revision. Every attempt should be made to retain the explanted device and return it to the Sponsor for evaluation.

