## **11.3 Sample Size and Power Analysis**

The original sample size in this study was 150 enrolled subjects. Additional proof testing and improvements in the device inspection process were employed during the study, at which time it was determined that an additional cohort of subjects was necessary. We are now comparing a cohort of subjects enrolled after these changes to the original cohort of subjects.

With an expected attrition rate of 10% per annum, this will yield an evaluable sample size of 52 shoulders at ten years ( $150 * 0.9^{10} = 52.3$ , where 0.9 or 90% is the number expected to be retained from one year to the next). Based on past experience, we may obtain clinical follow-up on this number of shoulders, but we may obtain radiographic follow-up on as few as two-thirds of these shoulders (about 35 shoulders). This remaining number of evaluable shoulders with clinical and radiographic follow-up is adequate to establish a reliable ten-year survival estimate of survival for hemi arthroplasty (Dorey and Amstutz, 1986).

For the new cohort, the sample size is calculated based on the non-inferiority of the study device. The success rate for the study device is 96.1% from the original population and is used as reference rate. Therefore, for a conservative success rate of 96.1% of the study device is used in the study. The non-inferiority margin  $\delta$  of -0.033 is chosen in the study. 212 subjects are required to achieve  $100(1 - \beta) \% = 80\%$  power to detect non-inferiority at the Significance level of  $\alpha = 0.05$ . To account for 10% lost to follow-up, the

total number of additional subjects is 237. Therefore, the estimated enrollment for the study will be 387 subjects.

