# 7 STATISTICAL ANALYSIS

## 7.1 General

Smith + Nephew's Global Biostatistics group will conduct the statistical analysis for this study. Unless otherwise stated, all significance tests and hypothesis testing will be two-sided, performed at the 5% significance level. Resulting p-values will be quoted and 95% two-sided confidence intervals will be generated where appropriate. All p-values will be rounded to three decimal places, p-values less than 0.001 will be presented as '<0.001' in all tables.

Where data summaries are specified, categorical and ordinal variables will be summarized with frequencies and percentages. Continuous variables will be summarized with the following summary statistics: number of observations, mean, median, standard deviation, minimum and maximum values. All analyses will be performed in SAS 9.4 (or later).

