## 7.2 Analysis Populations

The following subject populations will be used for the statistical analysis of this study.

- **Full analysis set population (FAS)**, following Intention to Treat principle including all subjects who are enrolled into the study.
- **Per-Protocol Population (PP)**, including all subjects in the full analysis set who have no significant protocol deviations and met the inclusion/exclusion criteria.
- **Per-Protocol Population 1(PP1)**, including all subjects in the full analysis set who have no significant protocol deviations and met the inclusion/exclusion criteria. This is the original cohort of subjects in the study who were enrolled prior to the additional proof testing and improvements in device inspection process. This population will be used for supporting analysis of the primary endpoint.
- **Per-Protocol Population 2(PP2)**, including all subjects in the full analysis set who have no significant protocol deviations and met the inclusion/exclusion criteria. This is the additional cohort of subjects who were enrolled after the additional proof testing and improvements in device inspection process. This population will be used for supporting analysis of the primary endpoint.

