## 7.3 Handling of Missing, Incomplete and Repeat Data

Data will be analysed as observed in the study database.

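### The 80% power in SAP 6.1 belongs to a different test: the primary test in SAP 7.9 has about 74% power at 387 without loss, and with loss its power depends on an unwritten scoring rule

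*SAP*

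**What the plan says.** **Sample size (SAP 6.1, copied from Protocol 11.3).** The calculation is for one cohort: "For the new cohort, the sample size is calculated based on the non-inferiority of the study device". Its inputs are a reference rate of 96.1%, an assumed true rate of 96.1%, a margin of 3.3 percentage points, a level of 0.05 with sidedness not stated, and 80% power. The result is 212 subjects. Then "To account for 10% lost to follow-up, the total number of additional subjects is 237", which with the original 150 makes 387. For the original cohort the same section reads: "With an expected attrition rate of 10% per annum, this will yield an evaluable sample size of 52 shoulders at ten years".

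**Test (SAP 7.1, 7.2, 7.9).** Unless stated otherwise, "all significance tests and hypothesis testing will be two-sided, performed at the 5% significance level". The primary endpoint is the 10-year success rate. Section 7.9 first declares success if the upper bound of the two-sided 95% interval for reference minus study rate is below 3.3%, which means a lower limit for the success rate above 92.8%. It later describes the interval for the rate as exact, and states the rule through the upper limit of the rate. The primary analysis set is the FAS, "following Intention to Treat principle including all subjects who are enrolled into the study". The new cohort on its own (PP2) is only summarised as an additional analysis.

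**Subjects without 10-year data.** SAP 7.3 says only: "Data will be analysed as observed in the study database". SAP 7.4 scores the first component of success by the absence of a removal or revision. Section 7.9 censors lost subjects, but only for Kaplan-Meier curves that are produced if the data allow. Under Protocol 7.0, if the "implant is removed then the Subject is considered revised, is withdrawn from the study, an Adverse Event and Study Completion CRFs must" be submitted, and "The remaining study-related follow-up visits are not required in the case of revision". Revised subjects therefore leave the study as recorded failures.

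**The concern.** The sample-size section and the analysis section differ in level, method and analysis set. A reader of 6.1 will conclude that the study has an 80% chance of success if the device performs at the reference rate. No section gives the power of the test that decides the study.

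Two further gaps make that power indeterminate. Attrition is 10% a year for one cohort and a flat 10%, with no period given, for the other, although both are followed for ten years. The scoring of a subject lost without a recorded event is also open. That second gap affects error control as well as power: if such subjects count as successes, failures after loss go unseen and a device at the unacceptable rate can pass too often.

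**Working it through.** **Inputs.** True rate 0.961, reference 0.961, margin 0.033, so threshold 0.961 − 0.033 = 0.928 (SAP 6.1, 7.9); 212, 237 and 387 subjects (6.1); two-sided 95% exact interval on the FAS (7.1, 7.9).

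**1. Reproducing the plan's figure.** One-sample normal approximation, n = (z_α + z_0.80)² × 0.961 × 0.039 / 0.033²:

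- one-sided 5%: 212.8, i.e. 212 truncated or 213 rounded up; 213/0.9 = 236.7, so 237
- one-sided 2.5% (the level of a two-sided 95% interval): 270.1
- null variance in the α term: 317.6 (one-sided 5%) or 411.7 (one-sided 2.5%)
- two-sample non-inferiority: 426 or 541 per arm

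Only the first gives 212.

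**2. Power of the planned test without loss.** Let f* be the largest number of failures for which the Clopper-Pearson two-sided 95% lower limit still exceeds 0.928. Power is P(failures ≤ f*) at a true rate of 0.961.

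| n | f* | Power |
|---|---|---|
| 387 (full FAS) | 17 | 74.4% |
| 390 | 18 | 80.8% |
| 348 (387 × 0.9) | 15 | 71.4% |
| 265 | 10 | 54.0% |
| 212 (sized cohort alone) | 7 | 41.3% |
| 135 (387 × 0.9¹⁰) | 3 | 22.4% |

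At n = 387, 17 failures give a lower limit of 93.06% and 18 give 92.75%. Exact power is saw-toothed: the mean over n = 372 to 402 is 77%, and the maximum for n from 100 to 387 is 79.0%, at 373.

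**3. Power with loss.** Assumptions, not in the plan: constant hazards, and loss independent of failure. Failure hazard −ln(0.961)/10; loss hazard −ln(r)/10, where r is the ten-year retention (0.9 or 0.9¹⁰). 400,000 simulated trials per case. Three attrition readings:

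- (i) flat 10% over ten years for everyone
- (ii) as stated for each cohort: 150 × 0.9¹⁰ + 237 × 0.9 = 52.3 + 213.3, about 265 (a sum made here, not a plan figure)
- (iii) 10% per year for everyone

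Three scoring rules:

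- A: recorded failures are kept; success requires 10-year follow-up
- B: failures and successes drop out equally (fixed n of 348, 265 and 135)
- C: every subject with no recorded event is a success

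| Rule | Power at 96.1%: (i) / (ii) / (iii) | False pass at 92.8%: (i) / (ii) / (iii) |
|---|---|---|
| A | 65% / 35% / 2% | 1.0% / 0.2% / under 0.1% |
| B | 71% / 54% / 22% | 1.8% / 1.5% / 1.1% |
| C | 81% / 92% / 99% | 3% / 12% / 53% |

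The cause is bias in the estimated rate. At a true 96.1% its mean is 95.9 / 95.4 / 93.3% under A and 96.3 / 96.8 / 97.6% under C.

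**4. Comparison with Kaplan-Meier.** This is not the planned test. Requiring the 10-year Kaplan-Meier lower limit (log-log Greenwood, 20,000 runs) to exceed 92.8% gives 75% power without loss and 73 / 65 / 46% with loss. False passes are 1.6% to 1.9%.

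**5. The literal upper-limit rule.** If the upper limit of the rate had only to exceed 92.8%, 349 of 387 (90.2%) would pass, and a device truly at 92.8% would pass about 98% of the time.

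**The case against.** - **The 74% depends on the exact method.** The first statement of the success rule in 7.9 names no method for the interval on the difference; the exact interval is described later, for the rate. At 387, a two-sided Wald interval gives 87% by binomial enumeration (92% by the normal formula), and an exact one-sided 5% limit also gives 87%. So neither level nor method alone brings power below 80%; the combination does. This is correct, and the 74% should be quoted with that condition. The exact interval is nevertheless the only one that the SAP names for the primary rate.
- **The shortfall without loss is modest.** It is three to six points, and 390 subjects would reach 80.8%. That stands. The 41% at 212 describes a test that 7.9 does not run; it shows only that the quoted power would not hold for the sized cohort either.
- **The origin of 212 is inferred.** The plan gives neither formula nor sidedness, and the match needs 212.8 truncated in one place and rounded up in the other. The sponsor should confirm it, although no other formula tried gives 212.
- **The loss figures are model outputs.** They change with the model. If every event in a lost subject goes unseen, rule C gives 86% power and 5.3% false passes at flat 10% loss, and over 99.9% and 99% at 10% per year. Scoring every lost subject as a failure gives power near zero. The individual percentages should not be leaned on. The spread is the finding.
- **96.1% may not be the true 10-year rate.** Exact power at 387 is 34% at a true 95%, 52% at 95.5% and 86% at 96.5%. The calculation uses the plan's own input, so it inherits that uncertainty.
- **The text in 6.1 is a quotation from the protocol and enrolment will not change.** True, but SAP 7.14 lists only the interim analysis as a change, so nothing tells the reader that the quoted power does not describe the test.

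**Conclusion.** The concern holds. The 212, 237 and 80% are internally consistent for a one-sided 5% normal approximation on the new cohort, but they do not describe the primary test. For the two-sided 95% exact test on 387 subjects, with no loss, a true rate of 96.1% and the lower-limit reading of 7.9, power is 74% (about 77% smoothed over neighbouring sample sizes).

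With loss, power runs from about 2% to 99% across the scoring rules A to C and the attrition readings considered, assuming constant hazards and independent loss. The rule that looks most favourable is also the one that loses control of false passes. The mismatch and the missing rule are certain from the text; the figures under loss are illustrative.

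**What to change.** 1. In SAP 7.9, reconcile the rule worded through the upper limit of the rate with the rule on the difference, so that a single decision rule remains.
2. In SAP 7.3 and 7.9, state how a subject lost before 10 years with no recorded event is scored in the primary test, and which attrition applies to each cohort over ten years.
3. Keep the quoted protocol text in 6.1 and, once the sponsor has confirmed the derivation, add after it:

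> The 212 evaluable (237 enrolled) subjects and the 80% power rest on a one-sample normal approximation at one-sided 5% for the new cohort alone, with a flat 10% loss. They do not apply to the primary test in 7.9, a two-sided 95% exact interval for the 10-year success rate on the FAS. For that test, with 387 subjects, no loss and a true rate of 96.1%, the power is about 74% (about 77% averaged over neighbouring sample sizes). With loss to follow-up the power is [value under the scoring rule and attrition stated in 7.3 and 7.9].

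The cost is SAP wording, one scoring decision that has to be made in any case, and a less favourable stated power. Enrolment and margin are unchanged.
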